#### “2.13.1 Incidence of adverse reactions by presence or absence of hepatic function disorder”

Patients included in analysis: Patients included in safety analysis

Objective of analysis: Occurrence status of adverse reactions by presence or absence of hepatic function disorder should be shown by dividing them into serious and non-serious ones.

Analysis items: Following items should be aggregated by presence or absence of hepatic function disorder in adverse reactions that occurred in the period included in safety analysis.

The number of patients, the number of patients in whom adverse reactions occurred, rate of patients in whom adverse reactions occurred, the number of adverse reactions, the number of patients in whom adverse reactions occurred and rate of these patients to those included in analysis by types of the reactions (SOC, PT) should be calculated.

Notes: The event with the highest seriousness of all the events with same PT in one patient should be included in analysis. When the number of patients for events included in analysis is counted, data should be made invalid according to patient number and seriousness, and when the number of SOC is calculated, data should be made invalid according to patient number, seriousness, and SOC for aggregation.

#### “2.13.5 Incidence of adverse reactions by presence or absence of moderate or higher degree central nervous lesion”

Patients included in analysis: Patients included in safety analysis

Objective of analysis: Occurrence status of adverse reactions by presence or absence of moderate or higher degree central nervous lesion should be shown by dividing them into serious and non-serious ones.

Analysis items: Following items should be aggregated by presence or absence of moderate or higher degree central nervous lesion in adverse reactions that occurred in

the period included in safety analysis.

The number of patients, the number of patients in whom adverse reactions occurred, rate of patients in whom adverse reactions occurred, the number of adverse reactions, the number of patients in whom adverse reactions occurred and rate of these patients to those included in analysis by types of the reactions (SOC, PT) should be calculated.

Notes: Notes for “2.13.1 Incidence of adverse reactions by presence or absence of hepatic function disorder by seriousness” should be referred to.

“2.14.1 Incidence of adverse reactions by presence or absence of renal impairment by seriousness”

Patients included in analysis: Patients included in safety analysis

Objective of analysis: Occurrence status of adverse reactions by presence or absence of renal impairment should be shown by dividing them into serious and non-serious ones.

Analysis items: Following items should be aggregated by presence or absence of renal impairment in adverse reactions that occurred in the period included in safety analysis.

The number of patients, the number of patients in whom adverse reactions occurred, rate of patients in whom adverse reactions occurred, the number of adverse reactions, the number of patients in whom adverse reactions occurred and rate of these patients to those included in analysis by types of the reactions (SOC, PT) should be calculated.

Notes: Notes for “2.13.1 Incidence of adverse reactions by presence or absence of hepatic function disorder by seriousness” should be referred to.

“2.16.1 Incidence of adverse reactions in elderly patients and that in non-elderly patients by seriousness”

Patients included in analysis: Patients included in safety analysis

Objective of analysis: Occurrence status of adverse reactions in elderly patients and that in non-elderly patients should be shown by dividing them into serious and non-serious ones.

Analysis items: In adverse reactions that occurred in the period included in safety analysis, following items should be aggregated according to whether the patients were elderly or not and by seriousness.

The number of patients, the number of patients in whom adverse reactions occurred, rate of patients in whom adverse reactions occurred, the number of adverse reactions, the number of patients in whom adverse reactions occurred and rate of these patients to those included in analysis by types of the reactions (SOC, PT) should be calculated.

Notes: Notes for “2.13.1 Incidence of adverse reactions by presence or absence of

hepatic function disorder by seriousness" should be referred to.

**“2.17 List of occurrence status of adverse reactions and infections in this survey”**

Patients included in analysis: Patients included in safety analysis

Objective of analysis: Occurrence status of adverse reactions and serious adverse reactions is shown.

Analysis items: In adverse reactions that occurred in the period included in safety analysis, adverse reactions and serious adverse reactions should be aggregated for following items.

The number of patients included in the survey, the number of patients in whom adverse reactions occurred, the number of adverse reactions, rate of patients in whom adverse reactions occurred, the number of patients in whom adverse reactions occurred and rate of these patients in those included in the survey by types of the reactions (SOC, PT) should be calculated.

Notes: If there are events with same PT in one patient, these events should be counted as 1 event (1 patient) according to following rules for seriousness.

Priority for seriousness: Serious > non-serious

**“2.18 List of occurrence status of adverse events in this survey”**

Patients included in analysis: Patients included in safety analysis

Objective of analysis: Occurrence status of adverse events, serious adverse events, and non-serious adverse events is shown.

Analysis items: Adverse events, serious adverse events, and non-serious adverse events should be aggregated for following items in adverse events that occurred in the period subject to safety analysis.

The number of patients, the number of patients in whom adverse events occurred, the number of adverse events, rate of patients in whom adverse events occurred, the number of patients in whom adverse events occurred and rate of these patients to those included in analysis by types of the events (SOC, PT) should be calculated.

Notes: If there are events with same PT in one patient, these events should be counted as 1 event (1 patient) according to following rules for seriousness.

Priority for seriousness: Serious > non-serious

**“2.19.1 Treatment for patients who showed insufficient response to treatment”**

Patients included in analysis: In patients included in safety analysis, patients who discontinued the survey because of “insufficient effect” or patients in whom dose or the number of administration was adjusted because of “insufficient effect” should be

included.

Objective of analysis: Presence or absence of drugs used after discontinuation of this drug and distribution of the drugs used after discontinuation of this drug are shown.

Analysis items: The number of patients included in analysis should be calculated.

The number of patients and rate of these patients by “drugs used after discontinuation of this drug” and ”detailed classifications of drug used after the discontinuation of this drug“ defined in “11 method of dividing hierarchy for data” should be calculated.

Date of patients in whom dose or the number of administration was adjusted because of “insufficient effect” should be obtained from “[HUMIRA BD] converted data for provision for analysis”.

Notes: Detailed classifications of drug used after the discontinuation of this drug may be overlapped.

“2.19.2 Dosage and administration for patients who showed insufficient response to treatment”

Patients included in analysis: In patients included in safety analysis, patients who discontinued the survey because of “insufficient effect” or patients in whom dose or the number of administration was adjusted because of “insufficient effect” should be included.

Objective of analysis: Distribution of dosage and administration for patients who showed insufficient response to treatment is shown.

Analysis items: The number of patients included in analysis should be calculated.

The number of patients and rate of these patients to those included in analysis should be calculated by presence or absence of discontinuation and classification of dosage and administration (patients discontinued by the initial or second administration, patients who received this drug 3 times or more, the maximum dose for the third or subsequent administration is 40 mg/2 weeks, 40 mg/1 week, 80 mg/2 weeks, 80 mg/1 week, 160 mg/2 weeks, 160 mg/1 week, and others). Items with the number of 0, output by items should not be made.

Date of patients in whom dose or the number of administration was adjusted because of “insufficient effect” should be obtained from “[HUMIRA BD] converted data for provision for analysis”.

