### 9.2. Descriptive statistics

Following values should be calculated for categorical data and quantitative data

Types of data	Data required to be calculated
Categorical data	
The number or rate of patients
 
When rate of patients is calculated, patients with “unknown” and “not described” data should be included in denominator.
 
In addition, breakdown of patients is displayed as rate, the number of

Types of data	Data required to be calculated
	patients including those with “unknown” and “not described” data from high-order items should be used as denominator. When test is performed, patients with “unknown” or “not described” data should be excluded.
Quantitative data	The number of patients, mean value, standard deviation, median value, the minimum value, and the maximum value should be applicable

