Presence or absence of implementation of endoscopy	
If at least one description of date between the start date of the initial administration of this drug and the last date of the final administration of this drug in implementation date of endoscopy in “level of improvement in endoscopy findings” in the survey sheet, endoscopy is deemed to have been implemented. If there is a check mark in a box for not implemented, endoscopy is deemed to have not been implemented. In any other situations, whether endoscopy has been implemented or not is deemed to be unknown/not described.
 
The site of endoscopy should be derived from data with check mark in “site of ulcer with the maximum diameter” in the survey sheet.

Presence or absence of drug used after discontinuation of administration of this drug	
If there is data with description in “drugs used after discontinuation of administration of this drug”, patients are deemed to have drugs after discontinuation of administration of this drug. If there is data about drugs used after discontinuation, patients are deemed to have drugs used after discontinuation of administration of this drug. If whether patients have drugs used after the discontinuation of administration of this drug or not is not described or cannot be assessed, presence or absence of drug used after the discontinuation of this drug is deemed to be unknown/not described, and in any other situations, patients are deemed to have no drug used after the discontinuation of administration of this drug.

Presence or absence of use of drug used after the discontinuation of administration of this drug (aminosalicylic acid preparation)	
If there is data about aminosalicylic acid preparation in “drugs used after the discontinuation of this drug” in the survey sheet, patients are deemed to have received aminosalicylic acid preparation, and in any other situations, patients are deemed to have not received aminosalicylic acid preparation.

Presence or absence of use of concomitant drug (steroid)	
If there is data with description in steroid in “drugs used after the discontinuation of this drug” in the survey sheet, patients are deemed to have received steroid, and in any other situations,

Name of data	Derivation and calculation method
	patients are deemed to have not received steroid.

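### Table 2.19.1 mixes patients who stopped the drug with patients who may still be on it, so its first-level rates of drug use after discontinuation are diluted and hard to read

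*SAP*

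**What the plan says.** SAP section 13.2 defines the population of Table 2.19.1 in two parts joined by 'or'. The first is "In patients included in safety analysis, patients who discontinued the survey because of" insufficient effect. The second is "patients in whom dose or the number of administration was adjusted because of" insufficient effect, and it does not require that the patient stopped. The objective is "Presence or absence of drugs used after discontinuation of this drug and distribution of the drugs used after discontinuation of this drug are shown". The only total requested is the pooled one: "The number of patients included in analysis should be calculated". Numbers and rates are then given by drug used after discontinuation and by its detailed classes. The denominator of those rates is not written out.

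Table 2.19.2 has the same population, but its numbers and rates "should be calculated by presence or absence of discontinuation and classification of dosage and administration".

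Section 10.1 derives the drug variable from the survey sheet. An entry gives 'present'. Where nothing is described or the matter cannot be assessed, "presence or absence of drug used after the discontinuation of this drug is deemed to be unknown/not described". Everything else counts as no drug. Section 11 lists absent, present, unknown and not described, with no class for a patient who has not stopped. Section 9.2 says that patients with unknown or not-described data "should be included in denominator".

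**The concern.** The item tabulated applies only to patients who stopped the drug, while the table population admits patients who may not have stopped. With no class of their own, continuing patients must fall into 'absent' or into unknown/not described.

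This has two consequences. The 'present' rate then depends partly on how many patients had their regimen adjusted and carried on, not only on what happened after stopping. The other rows also lose their meaning. 'Absent' merges patients who stopped and took nothing with patients still on the drug, and unknown/not described merges missing data with not applicable. SAP section 3.1 says that part or all of the results go into the report to the regulatory authority and the reassessment application, so the table may be read outside the study team.

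**Working it through.** The SAP gives no figure to reproduce, so the check is a comparison of the rules followed by simple algebra.

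**1. Does the population include patients who did not stop?** The second part of the population does not require stopping. Table 2.19.2 divides the same population by discontinuation status, so the SAP itself provides for both kinds of patient.

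**2. Where does a continuing patient go?** With no post-discontinuation drug entry, section 10.1 leaves only 'no drug' or unknown/not described. Section 11 offers no other class, and section 9.2 keeps the unknowns in the denominator.

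**3. What does the SAP do elsewhere?** In section 13.1 it restricts the denominator to patients to whom an item applies. Table 1.12.1 takes pregnancy/lactation over female patients. Table 1.13 takes self-administration error over patients who self-administer. Table 1.7 takes the presence of a recorded discontinuation reason over those who discontinued.

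**4. Effect on the first-level rate.** Let p be the share with a later drug among those who stopped, and s the share of the table population still on the drug. Taking the pooled group as denominator:

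reported 'present' rate = p × (1 − s)

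Both p and s are assumptions.

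| p | s = 10% | s = 25% | s = 50% | s = 75% |
|---|---|---|---|---|
| 60% | 54% | 45% | 30% | 15% |
| 80% | 72% | 60% | 40% | 20% |
| 100% | 90% | 75% | 50% | 25% |

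At s = 0 the reported rate equals p.

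**5. Example with assumed counts.** Take 20 patients who stopped, 16 of them with a later drug, and 20 adjusted patients still on the drug.
- Among stoppers: 16/20 = 80%.
- Over the pooled group: 16/40 = 40%.
- The absent and unknown rows together hold 40 − 16 = 24 patients. Of these, 20 are not applicable and only 4 stopped without a recorded later drug.

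**6. Detailed drug classes.** Section 9.2 takes breakdown rates over the higher-order item. The note to Table 1.12.1 gives the example of complication classes taken over patients who have complications. Applied here, the classes would be divided by the 16 patients with a drug present, whether or not the 20 continuing patients are in the table.

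**The case against.** **The denominator is inferred.** Table 2.19.1 does not say that its rates are taken over all patients included in the analysis, whereas Table 2.19.2 does. A reader might take the pooled denominator as a stated rule, but the SAP does not write it. It is the most natural reading of the population, the single total and section 9.2. If the denominator is instead undefined, that also needs correcting.

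**The pooled rate could be the intended quantity.** The table's title concerns patients with insufficient response, and the share of all such patients who moved to another drug is a legitimate description. This stands as far as the 'present' row goes. It does not help the 'absent' and unknown rows, which still combine different situations.

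**Some patients flagged as continuing can have a post-discontinuation drug.** Section 10.1 classes a patient as discontinued only if the last administration falls before start + 350, 700 or 1064 days, while follow-up runs to start + 364, 728 or 1092 days. A patient who stops in the last 14, 28 or 28 days is therefore flagged as continuing. The drug variable is set from the survey sheet without reference to that flag. One might infer that a patient classed as not discontinued can never have the outcome, but these definitions do not support that. The fix has to allow for it.

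**The drug distribution is probably sound.** A reader might infer that the whole table is diluted. Under the higher-order-item rule, the class rates are probably not.

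**The consequence is limited.** The table is descriptive, no test depends on it, and counts stand beside the rates. The discontinued count in Table 2.19.2 would let a reader roughly rebuild the 'present' rate. It would not let the reader sort the 'absent' and unknown rows by discontinuation status.

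**Conclusion.** The point holds for the first-level rows of Table 2.19.1. On the most natural reading, the rate of any later drug is multiplied by the share of the table population that stopped, and the 'absent' and unknown rows mix patients to whom the question does not apply with patients who took nothing or have missing data.

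The size cannot be stated from the SAP. It would be nil if every adjusted patient later stopped, and a halving if half of the table population were still on the drug. The conclusion rests on two conditions: that the pooled group is the denominator, and that at least some adjusted patients remain on treatment. The matter is worth correcting because the rates change and the remedy is simple, but it touches no hypothesis test.

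**What to change.** Keep the population of Table 2.19.1 and divide it by discontinuation status, as Table 2.19.2 does. Compute the rates of post-discontinuation drugs among all patients in the table who stopped the drug, whatever the recorded reason. Show continuing patients in a separate 'not discontinued' row outside the denominator. State both denominators in the text: stoppers for present/absent/unknown, and patients with a drug present for the detailed classes.

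For this table, count as stopped any patient with a recorded post-discontinuation drug or a discontinuation on the survey sheet, even where the date rule in section 10.1 classes the patient as continuing.

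Restricting the table to patients who stopped for insufficient effect is not advised. It would drop patients who were adjusted for insufficient effect and later stopped for another reason.

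The cost is a short change of SAP wording and a smaller denominator. The inputs are items that the SAP already draws from the survey sheet, so no new data are needed.

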### 13.3. Efficacy

“3.1 Level of overall improvement”

Patients included in analysis: Patients included in efficacy analysis

Objective of analysis: Level of overall improvement at the last follow-up is shown.

Analysis items: The number of patients included in analysis should be calculated.

The patients who achieved overall improvement and rate of these patients to those included in analysis based on the level of overall improvement calculated at last follow-up according to “12.3 Time of evaluation of level of overall improvement should be calculated by “The level of overall improvement” and “detailed classification of overall improvement at the level of improved or higher” defined in “11 method of dividing hierarchy of data”.

“3.1.1 Level of clinical improvement (level of improvement in endoscopy findings is “2. shrinkage” or lower and comprehensive evaluation of gastrointestinal symptoms is “1” or lower”

Patients included in analysis: Patients included in efficacy analysis

Objective of analysis: Level of clinical improvement is shown by time of evaluation.

Analysis items: The number of patients included in analysis, the number of patients who achieved clinical improvement and rate of these patients to those included in analysis should be calculated by the time of evaluation.

Notes: The number of patients should be that of patients with data of evaluation of endoscopy findings within relevant period subject to analysis and evaluation of gastrointestinal symptoms in 4 weeks before and after the date of implementation of endoscopy. Time Allowance for the time of evaluation should be according to “12.4. Rate of patients who achieved clinical improvement, rate of patients who achieved complete remission, and time of evaluation of level of improvement in endoscopy findings”.

“3.1.2 Rate of patients who achieved complete remission (level of improvement in endoscopy findings is “1. remission or scar” and comprehensive evaluation of gastrointestinal symptoms is “0” or lower”.

Patients included in analysis: Patients included in efficacy analysis

Objective of analysis: Level of complete remission is shown by time of evaluation.

Analysis items: The number of patients included in analysis, the number of patients who achieved complete remission and rate of these patients to those included in analysis should be calculated by the time of evaluation.

Notes: The number of patients should be that of patients with data of evaluation of endoscopy findings within relevant period subject to analysis and evaluation of gastrointestinal symptoms in 4 weeks before and after the date of implementation of endoscopy. Time Allowance for the time of evaluation should be according to “12.4. Rate of patients who achieved clinical improvement, rate of patients who achieved complete remission, and time of evaluation of level of improvement in endoscopy

findings”.

“3.2.1 Comprehensive evaluation of gastrointestinal symptoms at each time of evaluation”

Patients included in analysis: Patients included in efficacy analysis

Objective of analysis: Comprehensive evaluation of gastrointestinal symptoms is shown by time of evaluation.

Analysis items: The number of patients included in analysis, the number of patients have comprehensive evaluation of gastrointestinal symptoms (0,1,2,3,4) and rate of these patients to those included in analysis, the number of patients who achieved improvement in gastrointestinal symptoms and rate of these patients to those included in analysis should be calculated by time of evaluation.

Notes: Time Allowance at time of evaluation should be according to “12.5 Time of evaluation of gastrointestinal symptoms”. Only patients who have evaluation corresponding to administration start and Time Allowance of each time of evaluation should be included in analysis.

“3.2.2 Evaluation of gastrointestinal symptoms at each time of evaluation”

Patients included in analysis: Patients included in efficacy analysis

Objective of analysis: Evaluation of gastrointestinal symptoms is shown by time of evaluation.

Analysis items: The number of patients included in analysis, the number of patients who have evaluation of gastrointestinal symptoms (0,1,2,3,4) and rate of these patients to those included in analysis, the number of patients who achieved improvement in detailed classifications of gastrointestinal symptoms and rate of these patients to those included in analysis should be calculated by time of evaluation.

Notes: Time Allowance at time of evaluation should be according to “12.5 Time of evaluation of gastrointestinal symptoms”. Only patients who have evaluation corresponding to administration start and Time Allowance of each time of evaluation should be included in analysis.

“3.3.1 Level of improvement in endoscopy findings”

Patients included in analysis: Patients included in efficacy analysis

Objective of analysis: Level of improvement in endoscopy findings is shown by time of evaluation.

Analysis items: The number of patients included in analysis, the number of patients who achieved improvement in endoscopy findings and rate of these patients to those

included in analysis should be calculated by the time of evaluation.

Notes: Time Allowance for the time of evaluation should be according to “12.4. Rate of patients who achieved clinical improvement, rate of patients who achieved complete remission, and time of evaluation of level of improvement in endoscopy findings”. Patients who have evaluation corresponding to Time Allowance of each time of evaluation should be included in analysis.

